7.4. Level of Significance & Multiplicity Adjustment

To evaluate the efficacy of JZP385 at doses of 10, 20, and 30 mg/day compared with placebo, pairwise treatment difference between each of the 3 doses and placebo will be tested at the end of Week 12 for the primary and key secondary endpoints.

The family-wise Type I error rate will be controlled at a 2-sided significance level of 0.05. To address the multiplicity issue due to the multiple efficacy endpoints and doses, a fixed hierarchical testing sequence will be employed. The testing procedure will stop when a p-value exceeds 2-sided significance level of 0.05 (see below).

Statistical hypotheses to be tested (in sequential order):

- 1. Change in the TETRAS composite outcome score from Baseline to Week 12, 30 mg/day versus placebo.
- 2. Difference in proportion of participants who improved (≥ 1 point decrease) on the CGI-S from Baseline to Week 12, 30 mg/day versus placebo.
- 3. Change in the TETRAS composite outcome score from Baseline to Week 12, 20 mg/day versus placebo.
- 4. Difference in proportion of participants who improved (≥ 1 point decrease) on the CGI-S from Baseline to Week 12, 20 mg/day versus placebo.
- 5. Change in the TETRAS composite outcome score from Baseline to Week 12, 10 mg/day versus placebo.
- 6. Difference in proportion of participants who improved (≥ 1 point decrease) on the CGI-S from Baseline to Week 12, 10 mg/day versus placebo.

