9.1.3.1. Pattern Mixture Model

A control-based Pattern Mixture Model will be used to explore the possibility of data being MNAR for participants who discontinued early from study due to either lack of efficacy or an adverse event. For participants who early discontinued due to other reasons, missing data will be imputed assuming MAR. Control-based Imputation (CBI) method assumes a mean and variance based on the control group for participants who withdrew from the JZP385 group at the time of withdrawal to the imputed timepoint, with the observed values prior to withdrawal still considered, thus a slow decay back toward the control group mean eventually. (Carpenter JR, 2013) This method assumes that from withdrawal onwards, participants in the active treatment group will progress back to the participants in the control group.

Figure 2 illustrates MAR estimates versus the estimates derived from CBI (assuming study participants withdraw at Visit 2 and a lower response indicates improvement).

Figure 2 MAR vs CBI

The control-based imputation will be implemented through steps below:

Treatment dropouts and missing observations at Weeks 4, 8 and 12 will be imputed using the multiple imputation method. MI procedure in SAS will be used to impute the missing TETRAS composite outcome score at the missed visit to create 20 complete datasets.

The missing data pattern will be checked. If any non-monotone missing data pattern is observed, 2 separate steps will be followed to complete the imputation, starting with Step 1. If a monotone missing data pattern is observed, skip to Step 2 directly (set imputation number to 20 instead).

Step 1: the Markov Chain Monte Carlo (MCMC) method will be used with a single chain to impute TETRAS composite outcome score by treatment, baseline stratification group as well as baseline TETRAS composite outcome score to create 20 imputed datasets with monotone missing patterns. Set the seed as 8715942. Imputed scores should be rounded to nearest integer, with the minimum and maximum possible score set to 0 and 42 respectively, which corresponds to the range of possible TETRAS composite outcome score.

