9.2.2. Primary Analysis

The main estimator of the key secondary estimands will be analyzed using the CMH test adjusting for the stratification factor at randomization (Baseline TETRAS composite score: ≤ 17 or > 17 and antitremor medication use at Baseline: Yes or No). Number of responders in each group, proportion as well as 95% CI (Wilson score method) will be reported at Week 12. The 2-sided p-values from the CMH test, the unadjusted treatment difference as well as the adjusted treatment difference in proportion using the weighted average of the treatment differences across strata with CMH weights, and the associated 2-sided 95% CI using a normal approximation to the weighted average will be derived and reported at Week 12.

Treatment dropouts and missing observations for the main analytic approach will be handled through multiple imputation (MI), a method that relies on observed values from similar participants who remained in the study to bridge information to deduce missing observations. Missing values at Weeks 4, 8 and 12 for CGI-S will be imputed using the MI method. The MI procedure in SAS will be used to impute a missing CGI-S score at the scheduled visit to create 20 complete datasets.

The missing data pattern will be checked at Baseline, Weeks 4, 8 and 12. If any non-monotone missing pattern is observed, 2 separate steps will be followed to complete the imputation, starting with Step 1. If a monotone missing pattern is observed, skip to Step 2 (setting imputation number to 20)

Step 1: the Markov Chain Monte Carlo (MCMC) method will be used with a single chain to impute missing CGI-S scores by treatment, baseline stratification group as well as baseline CGI-S score to create 20 imputed datasets with monotone missing patterns. Set the seed as 8715942. Imputed scores should be rounded to nearest integer, set minimum and maximum possible score to 1 and 5 respectively, which corresponds to the range of CGI-S.

Step 2: the predictive mean matching (PMM) method will be used to impute the remaining missing CGI-S scores for the 20 imputed datasets with monotone missing patterns. The imputation procedure will use monotone statement to create 1 compete dataset for each of the monotone datasets from Step 1, with model variables include treatment, baseline stratification group, as well as CGI-S score at scheduled visits from Baseline to Weeks 4, 8 and 12. Set the seed as 4985135 and number of closest observations to 2.

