The imputed datasets will be analyzed using CMH test, and the final inference will be pooled using SAS procedure MIANALYZE.

The following is an example SAS code for CMH analysis:

PROC SORT DATA = CGIS;

```
Jazz Pharmaceuticals
Statistical Analysis Plan - Protocol JZP385-201
BY IMPUTESEO VISIT TRT STRATUM DECENDING RESPONSE:
RUN;
PROC SQL;
CREATE TABLE ADDIN AS
SELECT DISTINCT IMPUTESEQ, VISIT, TRT, STRATUM, 1 AS RESPONSE
FROM CGIS;
QUIT;
DATA CMH;
MERGE CGIS (IN=A) ADDIN (IN=B);
BY IMPUTESEQ VISIT TRT STRATUM DECENDING RESPONSE;
IF B AND NOT A THEN WGT = 0;
ELSE WGT = 1;
RUN:
*Adjusted (Stratified) Difference and CMH TEST;
PROC FREQ DATA=CMH;
BY IMPUTESEO AVISITN:
TABLES STRATUM*TRT*RESPONSE/RISKDIFF (COMMON CL=(NEWCOMBE)) CMH;
WEIGHT WGT/ZEROS;
RUN;
*Unadjusted (Unstratified) Difference;
```

PROC FREQ DATA=CMH;
BY IMPUTESEQ AVISITN;
TABLES TRT*RESPONSE/RISKDIFF CMH;

WEIGHT WGT/ZEROS;

RUN;

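### With 20 imputations, a CGI-S p-value close to 0.05 can fall on either side of the gate by the arbitrary seed; raising the number to 200–500 is a cheap, minor improvement

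*SAP*

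**What the plan says.** SAP 9.2.2 handles missing CGI-S scores by multiple imputation: "The MI procedure in SAS will be used to impute a missing CGI-S score at the scheduled visit to create 20 complete datasets". Step 1 uses MCMC ("Set the seed as 8715942") and Step 2 uses predictive mean matching ("Set the seed as 4985135 and number of closest observations to 2"). Then: "The imputed datasets will be analyzed using CMH test, and the final inference will be pooled using SAS procedure MIANALYZE". The SAP does not say on what scale the CMH result is pooled.

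SAP 7.4 places CGI-S at 30, 20 and 10 mg as tests 2, 4 and 6 of six. Its rule is: "The testing procedure will stop when a p-value exceeds 2-sided significance level of 0.05". Failure at test 2 therefore ends confirmatory testing of the TETRAS composite at 20 and 10 mg, and failure at test 4 ends it at 10 mg. Test 6 is last and gates nothing.

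The protocol (9.4.3.1) specifies two-step multiple imputation without a number of imputations. Neither document gives a reason for 20, a check of Monte Carlo error, or a rule for a p-value close to the threshold.

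SAP 9.1.3.1 also uses 20 datasets, but for a sensitivity analysis of the primary endpoint. The main analysis of that endpoint (SAP 9.1.2) is an MMRM without imputation.

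**The concern.** Twenty imputations are usually enough for an efficient estimate. A hard threshold on the p-value asks for more, because the pooled test statistic carries random error from the imputation draws. With another seed, equally valid, the same trial data would give a somewhat different p-value. Most of the time this does not matter. When p is close to 0.05 at test 2 or test 4, the seed can decide whether the primary endpoint at the lower doses may be claimed as confirmatory. The plan expects 20% dropout and analyses all randomized participants (SAP 5.3, 7.6), so a real share of the Week 12 CGI-S data will be imputed.

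**Working it through.** **Inputs from the documents.** Response 66% versus 40%; 80 evaluable and 100 randomized per arm; 20% dropout; stated power 91.7% (SAP 5.3). m = 20 imputations (SAP 9.2.2). Two-sided 0.05 at each step (SAP 7.4).

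**Assumptions.** The fraction of missing information (FMI) is not in the documents; I take 0.10 to 0.20. A simulation of the imputation (100 per arm, four strata, five-level CGI-S, 20% monotone dropout, two-donor matching, visit correlation 0.4 or 0.7) gave 0.11 to 0.17. Pooling is by Rubin's rules on an approximately normal scale such as the risk difference.

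**1. The plan's own figure.** Pooled SE = √(2 × 0.53 × 0.47/80) = 0.0789. Unpooled SE = √(0.66 × 0.34/80 + 0.40 × 0.60/80) = 0.0762. Power = Φ((0.26 − 1.96 × 0.0789)/0.0762) = Φ(1.38) = 0.917. This reproduces the stated 91.7%.

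**2. Monte Carlo SD of the pooled z.** s ≈ √(FMI/m). At m = 20, s = √(0.10/20) = 0.071, √(0.15/20) = 0.087 and √(0.20/20) = 0.100.

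**3. Spread of p when the limiting p (unlimited imputations) is 0.050.** The range is the two-sided p at z = 1.96 ± 2s.

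| FMI | m = 20 | m = 200 | m = 500 |
|---|---|---|---|
| 0.10 | 0.036–0.069 | 0.045–0.055 | 0.047–0.053 |
| 0.15 | 0.033–0.074 | 0.044–0.057 | 0.046–0.054 |
| 0.20 | 0.031–0.078 | 0.043–0.058 | 0.046–0.055 |

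**4. How often the decision changes.** Step 3 is conditional on the worst point, so it has to be averaged over trial results. Let the limiting z be normal with mean μ and SD 1. The chance that m imputations and unlimited imputations disagree at 1.96 is the integral of φ(z − μ) × Φ(−|z − 1.96|/s) over z. For small s this is close to 0.798 × s × φ(μ − 1.96).

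- Planned effect: 91.7% power gives μ = 1.960 + 1.385 = 3.345, and φ(1.385) = 0.153. At FMI 0.15 and m = 20: 0.798 × 0.087 × 0.153 = 0.011.
- Least favourable case: μ = 1.96, and φ(0) = 0.399. At FMI 0.15 and m = 20: 0.798 × 0.087 × 0.399 = 0.028.

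The integral over FMI 0.10 to 0.20 gives, per test:

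| | m = 20 | m = 200 | m = 500 |
|---|---|---|---|
| Planned effect | 0.9–1.2% | 0.3–0.4% | 0.2% |
| Least favourable effect | 2.3–3.2% | 0.7–1.0% | 0.5–0.6% |

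**5. Simulation check near the threshold.** The simulated datasets with a limiting p of 0.044 to 0.047 fell on the wrong side of 0.05 for 35 to 41% of redraws at m = 20, 15 to 24% at m = 100 and 1 to 4% at m = 500. One with a limiting p of 0.0494 still fell on the wrong side in 38% of redraws at m = 500.

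**The case against.** The strongest reply is that nothing here is an error. Both seeds are written into the SAP, so the result is reproducible and no analyst can pick a favourable one. Rubin's rules, as MIANALYZE applies them, already add a variance term for a finite number of imputations. Twenty is adequate for efficiency. The chance of p between 0.03 and 0.07 is about 6% per test at the planned effect and at most about 14%, and test 2 is reached only if test 1 succeeds. All of this stands, and it is why the point is minor. Fixing the seed makes the outcome reproducible; it does not make it less arbitrary.

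It may also be said that the non-responder imputation and the two-dimensional tipping-point grid (SAP 9.2.3) would expose a fragile result. They involve no random draws, but they test assumptions about missing data and do not decide the gate.

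A reader might infer three stronger things. One is that 20 imputations inflate the type I error; the noise moves results in both directions, and no inflation is shown. Another is that the primary endpoint depends on the seed; its main analysis uses no imputation. The third is that a failed CGI-S test would leave the lower doses unanalysed; SAP 9.1.2 reports the estimate, confidence interval and p-value for JZP385 versus placebo without making them conditional on the sequence, so what is lost is confirmatory status.

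**Conclusion.** The point holds as a cheap improvement, not as a flaw that threatens the trial. At m = 20 the seed changes the decision at 0.05 in about 1% of trials per test at the planned effect, and in at most about 3%. Only tests 2 and 4 carry consequences for later tests. These figures rest on an assumed FMI of 0.10 to 0.20, on pooling on an approximately normal scale that the SAP does not name, and on taking the planned power as that of the imputed analysis. At FMI 0.30 the m = 20 figures would be 1.5% and 3.9%.

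**What to change.** Before unblinding, change 20 to at least 200, preferably 500, throughout SAP 9.2.2: the opening statement, the instruction for a monotone pattern, and Steps 1 and 2. Keep both stated seeds.

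The same change in SAP 9.1.3.1 is optional, for consistency. That analysis gates nothing, although the tipping-point search in SAP 9.1.3.2 reuses its Steps 1 and 2 and works at the 0.05 boundary by design.

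The cost is computing time (500 imputations with their analyses took under one second for one comparison in Python) and a small revision of a final SAP. Nothing in the protocol conflicts with it. No number of imputations settles a limiting p almost exactly at 0.05.

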7.1. Discontinuation of Study Intervention

In rare instances, it may be necessary for a participant to permanently discontinue study intervention. If study intervention is permanently discontinued, the participant will not remain in the study. See the SoA for data to be collected at the time of discontinuation of study intervention and follow-up and for any further evaluations that need to be completed.

A participant must be discontinued from study intervention for any of the following reasons:

- The participant or participant's legal representative requests to discontinue study intervention.
- The participant has an AE that may compromise the participant's continued participation.
- The participant has a suicide risk reported or assessed by the Columbia Suicide Severity Rating Scale (C-SSRS; see Section 8.3.6).
- The participant has a positive serum pregnancy test or becomes pregnant during the study (see Appendix 5 and Section 8.3.5).
- The participant is noncompliant with study intervention or procedures.
- Sponsor decides to terminate the study prior to completion.

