9.4.1.4. Dropouts and Missing Data

The TETRAS composite outcome score will be derived as the sum of items 1 to 11 of the ADL section of TETRAS plus the sum of items 6 (left and right) and 7 of the PS section of the TETRAS (for a total of 14 items on the composite primary outcome). If \leq 3 items of the TETRAS composite outcome score are missing at a specific time point, the mean of the remaining non-missing TETRAS composite outcome score item scores at that point will be used to impute the missing TETRAS composite outcome score item value. The TETRAS composite outcome score will then be calculated as the sum of the observed and imputed item scores. If \geq 4 items of the composite primary outcome are missing, the TETRAS composite outcome score will not be calculated.

For the analysis of the TETRAS composite outcome score, the primary analysis will rely on MMRM, assuming participants who early discontinue the study intervention (defined as an intercurrent event) or missed the assessments due to other reasons would have efficacy outcomes like other participants in their treatment group, randomization stratum, and initial trajectory who completed the study. Sensitivity analyses will adopt control-based drop-out imputation methods to assess the impact on the treatment effect of JZP385 when underlying missing at random (MAR) assumption on the primary MMRM analysis shifted accordingly. A tipping point analysis will further assess the robustness of the primary analysis method.

For the analysis of CGI-S, the primary analysis will adopt a 2-step multiple imputation method and assume data to be missing at random. A tipping point analysis will be conducted as sensitivity analysis to assess the robustness of the primary analysis method.

The details will be further described in the SAP.

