7.2.3. Visit Windows

All scheduled, unscheduled, and early termination assessments will be summarized by derived analysis visit per the Table 5, regardless of whether the visit was performed on-site or remotely. Visit dates will be mapped based on the scheduled Period of each visit, with adjusted analysis-defined visit windows as specified in Table 5.

Table 5 Visit Windows for Assessments or Measurements

Study Period	Scheduled Visit	Scheduled Study Day	TETRAS-ADL, TETRAS-PS, CGIs	CGIc and PGIc	QUEST, SF-36v2, ETEA	C-SSRS ^b , Clinical Laboratory ^{c, e} , Urinalysis ^e , Weight, Vital Signs, Breath Alcohol ^{d, e} , ECG, Urine Pregnancy test
Screening	Visit 1/Visit 2 ^a	-49 to -8	Any Day up to -2	na	n/a	Any Day up to -2
Baseline ^f	Baseline Visit	-1	Closest prior to dosing	na	Closest prior to dosing	Closest prior to dosing
	Week 1	7 (-1, +2)	na	na	na	2 - 14
Double-Blind	Week 4	28±3	2 - 42	2 - 42	na	15 - 42
Treatment	Week 8	56± 3	43 - 70	43 - 70	na	43 - 70
	Week 12	84± 3	71 - 98	71 – 98	2 - max	71 - max
Safety Follow-up	End of Study	98± 3	na	na	2 - max	2 – max ^f

^a Screening Visit 2 is only for participants who need to wash out of any medications that impact tremor (e.g., anti-tremor medications) prior to Baseline;

^b At screening visit 1, C-SSRS screening/baseline version, at screening visit 2, C-SSRS since last visit version;

^c Clinical laboratory includes hematology and chemistry labs;

^dBreath Alcohol is not collected at W1;

^e Not collected at Safety Follow-up.

^f For participants who randomized without taking the study intervention, the Baseline Visit or latest Screening Visit (if Baseline Visit is not available) will be mapped.

If multiple assessments or measurements are recorded within a single visit window (including scheduled, unscheduled, repeated, and retest assessments or measurements as well as early discontinuation data), the following rules will be applied to determine the result from which assessment will be used for the summaries for that analysis visit.

- The priority will always be given to the scheduled visit within the corresponding visit window (e.g., scheduled W4 visit corresponds to Week 4 visit window) regardless of the relative distance to the scheduled Visit Day.
- If there are 2 or more observations within the same visit window, then the non-missing one closest to the scheduled Visit Day will be used in the analysis.

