Step 2: the predictive mean matching (PMM) method will be used to impute the remaining missing scores for the 20 imputed datasets with monotone missing patterns. The imputation procedure will use monotone statement to create 1 compete dataset for each of the monotone datasets from Step 1, with model variables to include treatment, baseline stratification group, as well as TETRAS composite outcome score at scheduled visits from Baseline to Weeks 4, 8 and 12. Set the seed as 4985135 and number of closest observations to 2.

For participants who discontinued the study early due to either lack of efficacy or an adverse event, the post-discontinuation values imputed through Steps 1 and 2 will be set to missing and rederived using CBI method (MNAR).

The imputed datasets with a mixture of MAR and MNAR imputations will be analyzed separately using the MMRM model specified in 9.1.2, then final inference will be pooled using the MIANALYZE procedure and reported.

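### The key secondary CGI-S imputation model leaves out the continuous and post-baseline TETRAS scores; adding one would ease the missing-at-random assumption at little cost, for a modest gain

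*SAP*

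**What the plan says.** Protocol 9.4.1.4 states that for CGI-S "the primary analysis will adopt a 2-step multiple imputation method and assume data to be missing at random". SAP 9.2.2 gives the details. Step 1 (MCMC, for intermittent gaps) is to "impute missing CGI-S scores by treatment, baseline stratification group as well as baseline CGI-S score". Step 2 (predictive mean matching with 2 donors) works "with model variables include treatment, baseline stratification group, as well as CGI-S score at scheduled visits from Baseline to Weeks 4, 8 and 12". The procedure is meant to "impute a missing CGI-S score at the scheduled visit to create 20 complete datasets".

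The strata used in the same section are "Baseline TETRAS composite score: ≤ 17 or > 17 and antitremor medication use at Baseline: Yes or No", so a dichotomised baseline TETRAS score is in the model. No continuous and no post-baseline TETRAS score enters either step.

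TETRAS and CGI-S are scheduled together at Baseline, Weeks 4, 8 and 12 and the Early Discontinuation Visit (Protocol 1.3). They share one analysis-window column, headed "TETRAS-ADL, TETRAS-PS, CGIs" (SAP 7.2.3). Protocol 7.1 adds: "If study intervention is permanently discontinued, the participant will not remain in the study".

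**The concern.** Under the hypothetical strategy, outcomes after discontinuation are imputed, and discontinuers leave the study. The imputation model therefore bears directly on the three CGI-S tests in the fixed sequence (hypotheses 2, 4 and 6 in SAP 7.4), with 20% dropout planned.

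CGI-S is a coarse predictor of its own future. It has five levels, and entry requires at least a moderate rating, so baseline takes only the values 3 to 5. The TETRAS composite runs from 0 to 42 and measures related disability. Lack of efficacy is a named reason for discontinuation, and a participant's TETRAS course may well reflect it. If dropout depends on TETRAS beyond what CGI-S shows, the data can be missing at random given everything the trial collects, yet not given the variables in this model. What is at stake is some avoidable bias, and some avoidable noise in the imputed values, in a type I error-controlled comparison.

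**Working it through.** **Inputs.** From SAP 5.3: 66% v 40% responders, 80 evaluable and 100 randomized per arm, 20% dropout, two-sided 0.05. From SAP 9.2.2: 20 imputations, 2 donors. The documents give no CGI-S/TETRAS correlation and no dropout mechanism; both were assumed and varied.

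**1. The plan's own figure.** Pooled-variance chi-square power is Φ[(δ√n − 1.96·√(2·p̄·q̄)) / √(p₁q₁ + p₂q₂)]. With δ = 0.26, n = 80 and p̄ = 0.53, this is Φ[(2.3255 − 1.3834)/0.6815] = Φ(1.382) = 91.66%. The stated 91.7% is reproduced.

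**2. Ceiling on any precision gain.** SE = √[(0.66×0.34 + 0.40×0.60)/n]. With 80 per arm this is 0.0762; with 100 per arm it is 0.0681. Recovering every missing outcome would cut the SE by 1 − 0.0681/0.0762 = 10.6%. No imputation model can reach that.

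**3. What earlier TETRAS adds to prediction.** With a CGI-S autocorrelation of 0.6, the R² for Week 12 CGI-S goes from 0.49 to between 0.49 and 0.52. In the most favourable case (autocorrelation 0.4) it goes from 0.27 to 0.33.

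**4. Bias when dropout depends on TETRAS.** Four simulation set-ups used 100 per arm, 2 donors and 20 imputations, with and without earlier TETRAS in the model. Set-up A used an assumed correlation matrix (300–400 trials per case). B (720 trials per case), C and D (400 each) used latent-severity models. Bias in the risk difference, in percentage points:

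| Set-up | SAP model | With TETRAS | Reduction |
|---|---|---|---|
| A | −0.51 to +0.33 | −0.59 to +0.24 | none consistent |
| B, weaker CGI-S | −0.87 | −0.43 | 0.44 |
| B, stronger CGI-S | −0.73 | −0.43 | 0.30 |
| C, moderate dropout link | −0.5, −0.6 | −0.15, −0.3 | 0.35, 0.3 |
| C, strong dropout link | −1.7, −1.9 | −0.6, −0.6 | 1.1, 1.3 |
| D, weaker CGI-S | −0.64 | −0.32 | 0.32 |
| D, stronger CGI-S | −0.41 | −0.36 | 0.05 |

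Monte Carlo SEs were 0.11 (B), 0.15–0.21 (C) and about 0.15–0.18 (D). The strong case in C had 19% v 30% missing, with placebo above the planned 20%. In C, a pure-noise covariate in place of TETRAS did not reduce the bias (−0.7 and −0.9 moderate; −2.0 and −2.1 strong). When dropout did not depend on TETRAS, bias in B was about −0.2 under both models, and in C it was 0.0 to −0.2. Against the SE of 7.6 points in step 2, a 0.5-point change is 0.5/7.6 = 0.07 SE and a 1.3-point change is 0.17 SE.

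**5. Pooled standard error.** The direction is not stable:
- A: ratio 0.978–0.987 with TETRAS, but 0.986–0.987 with pure noise, leaving 0–1% attributable to TETRAS.
- B: 0.0743 to 0.0727 and 0.0732 to 0.0717, reductions of about 2%, with no noise control.
- C: between no gain and about 2%.
- D: a rise of 1.1–1.7% with TETRAS, and of 1.9–2.6% with noise. A fifth run also showed a slight rise (about 1–3% over D and this run).

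**6. Actual spread and distance from the complete-data estimate.** The empirical SD fell by 4.5–7% in D (noise 4–6%) and by about 7–12% in the fifth run (noise 5–9%). The distance from the same trial's complete-data estimate fell by 13–28% in C, always more than with noise, and by 5–18% in the fifth run, usually more than with noise.

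**7. Power.** In B, power changed by 0 to 1.4 points.

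**The case against.** The strongest opposing case has four parts.

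- **The model is not bare.** It holds arm, antitremor use and dichotomised baseline TETRAS. CGI-S at an Early Discontinuation Visit is mapped into the analysis windows, so deterioration at withdrawal is partly captured, and such a visit on Days 71–98 can itself supply Week 12. This stands. It also means that the 20% planning rate need not equal the Week 12 missing rate.
- **Imputing an outcome from its own history is the SAP's consistent style.** The composite is imputed in the same way in SAP 9.1.3.1, using stratum and arm "as well as TETRAS composite outcome score at scheduled visits from Baseline to Weeks 4, 8 and 12". This stands: the choice is conventional and contradicts nothing in the protocol.
- **SAP 9.2.3 and 9.2.4 already add non-responder imputation, a two-dimensional tipping-point grid and a completers analysis.** Any shift in responder counts lies within that grid. This stands in part: those analyses show how fragile the result is, but none re-estimates the effect under a better-conditioned missing-at-random model.
- **The bias is small and runs toward no effect where TETRAS helps.** This stands, and it limits the point to a refinement.

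A reader might infer that the plan reports a larger standard error than it needs to. The evidence does not support this. A noise covariate reproduces most of the apparent gain, plausibly by breaking donor ties on a 5-point scale, and in two runs the pooled SE rose. A reader might also infer that Week 12 TETRAS could stand in for Week 12 CGI-S. For participants who leave the study it is normally missing as well, so the useful scores are the earlier ones.

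**Conclusion.** The omission is real, and the improvement is worth making. Missing-at-random is assumed given arm, stratum and CGI-S history only, although finer measurements from the same visits are available. The expected benefit is modest: about 0 to 0.5 percentage points less bias toward no effect under moderate TETRAS-driven dropout, about 1 point if that dropout is strong, estimates somewhat closer to the complete-data result, and 0 to 1.4 points of power. The bias reduction was not seen in every set-up. All these figures depend on assumed correlations and dropout mechanisms, and the set-ups simplify the plan; set-up A, for example, had one stratification factor and no intermittent gaps.

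The documents do not support calling the key secondary analysis invalid, or suggesting that it risks a false positive CGI-S result. This is an inexpensive refinement, not an error.

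**What to change.** In both Step 1 and Step 2 of SAP 9.2.2, add one TETRAS score at Baseline and Weeks 4 and 8 as an auxiliary variable, imputed in visit order before CGI-S at the next visit. Amending Step 2 alone is not enough, because intermittent gaps in the auxiliary score must also be filled.

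Use one score on one scale throughout. The sum of modified TETRAS-ADL items 1 to 11 (range 0 to 33 by SAP 9.1.1) is suitable, because Protocol 1.3 rules out only TETRAS-PS at remote visits. Do not switch between the 0–42 composite and the 0–48 TETRAS-ADL score within one covariate. State the bounds for the added score in Step 1, as is already done for CGI-S.

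The estimand, CMH test and testing sequence do not change, and no new data are needed. The cost is SAP wording, some programming and a somewhat larger imputation model. If Step 1 is run separately in each arm-by-stratum cell, the average cell holds 400/(4×4) = 25 participants, which is a reason to add one score and not several. If the main analysis is to stay as written, the same model could be pre-specified as a supplementary multiple-imputation analysis.
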